1.5. Risk/Benefit Assessment for the Study

Potential risks associated with the study include AEs, including ISRs with SC administration of LEN, infusion-related reactions, and antidrug antibody (ADA)-mediated reactions from GS-5423 and GS-2872. Administration of anti-HIV-1 bNABs, including GS-5423 and GS-2872, as well as the original bNABs on which they are based (3BNC117 and 10-1074), have been previously evaluated in humans. As observed with other mAbs, anti-HIV-1 bNABs were generally considered safe and well tolerated, and infusion-reactions were more common for mAbs that contained murine elements, compared with fully human mAbs like GS-5423 and GS-2872. Clinical monitoring for possible immunologic symptoms will be conducted during and immediately following bNAB infusion, and study sites are required to have appropriate supportive medications available, including, but not limited to, diphenhydramine, acetaminophen, and glucocorticoids during IV infusions; and to follow a protocol-specified management plan for infusion-related reactions.

In general, risks include those associated with frequent clinic visits and laboratory blood draws, and the associated pain and discomfort of multiple phlebotomies. Strategies to mitigate any potential risks include close monitoring of laboratory values as well as AEs. Parameters for monitoring of AEs will be well defined and closely followed.

A potential risk of virologic breakthrough with exposure to suboptimal therapeutic concentrations of the study drugs or unrecognized preexisting resistance to GS-5423, GS-2872, and/or LEN is the possible development of resistance to 1 or more study drugs. Data are limited to inform whether the protocol's application of resistance testing for bNABs can minimize this risk. A low rate of viral rebound was observed in Study GS-US-536-5816, which utilized the same sensitivity criteria as will be used in this study, suggesting that the study drugs will provide appropriately high efficacy in the study population. Strategies to further mitigate the risk for resistance include frequent assessments of HIV-1 RNA to ensure that virologic breakthrough is rapidly identified, thus limiting the time during which drug resistance mutations could emerge and data monitoring committee (DMC) futility assessments to identify and potentially discontinue treatment arms, thereby limiting the number of participants exposed to a treatment group that poses a risk to safety or efficacy. Each component of the study drugs is from a novel class without any known or predicted cross-resistance with currently approved ART, thus the development of resistance to any component of the study drugs would have limited impact on a participant's future treatment options.

The potential direct benefits of the study include a long-acting regimen that is administered once in 6 months rather than daily, thus freeing participants from the requirement of daily adherence to ensure efficacy. Participants may benefit from the novel bNAB containing regimen due to enhanced engagement of the immune system, reduction of the latent viral reservoir and/or improved immunologic control of HIV-1, but the magnitude and clinical importance of these potential effects have not been determined. Potential benefits to participants also include the use of bNABs, which may result in reduced risk of end-organ toxicities associated with some ART, and the participant's contribution to understanding the safety and tolerability of a novel long-acting treatment strategy including the PK of the regimen and contributions to helping develop new classes of ART with potential application for HIV-1 treatment, prevention, and cure.

An unanticipated event such as a disaster or public health emergency may pose additional potential risks to participants such as adequate study drug availability, interruptions to the study visit schedule, and adherence to protocol-specified safety monitoring or laboratory assessments. Refer to Appendix 11.2 for further details on the risks and risk mitigation strategy.

Considering the above, the benefit-risk balance for this study is considered positive.

1.6. Compliance

This study will be conducted in compliance with this protocol and in accordance with the ethical principles that have their origin in the Declaration of Helsinki and that are consistent with International Council for Harmonisation (ICH) Good Clinical Practice (GCP) and applicable regulatory requirements.

2. OBJECTIVES AND ENDPOINTS

Primary Objective	Primary Endpoint

 To evaluate the efficacy of switching to a regimen of LEN, GS-5423, and GS-2872 versus continuing on baseline oral ART as determined by the proportion of participants with HIV-1 RNA ≥ 50 copies/mL at Week 26 	
 Proportion of participants with HIV-1 RNA ≥ 50 copies/mL at Week 26 as determined by the US FDA-defined snapshot algorithm
Secondary Objectives	Secondary Endpoints

 To evaluate the efficacy of switching to a regimen of LEN, GS-5423, and GS-2872 versus continuing on baseline oral ART as determined by the proportion of participants with HIV-1 RNA ≥ 50 copies/mL at Week 52 To evaluate the efficacy of switching to a regimen of LEN, GS-5423, and GS-2872 versus continuing on baseline oral ART as determined by the proportion of participants maintaining virologic suppression (HIV-1 RNA < 50 copies/mL) at Weeks 26 and 52 To evaluate CD4+ T-cell counts at Weeks 26 and 52 To evaluate the safety and tolerability of the 2 treatment groups To evaluate the PK of GS-5423, GS-2872, and LEN To evaluate the immunogenicity of GS-5423 and GS-2872 	
 Proportion of participants with HIV-1 RNA ≥ 50 copies/mL at Week 52 as determined by the US FDA-defined snapshot algorithm Proportion of participants with HIV-1 RNA < 50 copies/mL at Weeks 26 and 52 as determined by the US FDA-defined snapshot algorithm Changes from baseline in CD4+ T-cell counts at Weeks 26 and 52 Proportion of participants experiencing TEAEs Trough concentrations at Weeks 26 and 52 and PK parameters (AUC_{0-t}, AUC_{last}, $t_{1/2}$, C_{max}, and T_{max}) for GS-5423, GS-2872, and LEN as appropriate Incidence of anti-GS-5423 and anti-GS-2872 antibodies

CCI

3. STUDY DESIGN

3.1. Study Design Overview

This is a Phase 2, randomized, open-label, active-controlled, multicenter study to evaluate the safety and efficacy of the long-acting regimen of LEN, GS-5423, and GS-2872. The study will include approximately 75 participants with sensitivity to GS-5423 and GS-2872 by protocol-defined criteria, who meet all eligibility criteria, and who will be randomized without stratification in a 2:1 ratio to Treatment Groups 1 and 3. Eligible participants have the option of participating in a study extension phase after completing study follow-up through Week 52.

3.1.1. Randomized Phase

Treatment Group 1

Participants in Treatment Group 1 will receive the long-acting regimen consisting of LEN, GS-5423, and GS-2872.

Participants will discontinue their baseline oral ART following administration of the complete study drugs on Day 1 (SC LEN 927 mg, oral LEN 600 mg, and IV infusions of GS-5423 and GS-2872), and will self-administer oral LEN 600 mg at home on Day 2. Participants will also receive study drug (SC LEN and IV infusion of GS-5423 and GS-2872) at Week 26.

All participants in Treatment Group 1 will return to the study center for visits at Weeks 4, 12, 24, 26, 38, 50, and 52.

Treatment Group 3

Participants in Treatment Group 3 will continue their baseline oral ART through Week 52. After Day 1, participants in Treatment Group 3 will return to the study center for visits at Weeks 12, 26, 38, 50, and 52.

3.1.2. Extension Phase

Treatment Group 1

At Week 52, participants in Treatment Group 1 who receive the study drug of LEN, GS-5423, GS-2872, and complete the study through Week 52 with HIV-1 RNA < 50 copies/mL at the preceding Week 50 visit, will be given the option to participate in the study extension phase. In the study extension phase, participants will continue to receive their randomized study drugs every 26 weeks.

Participants who elect not to participate or are not eligible to participate in the extension phase will resume their baseline oral ART (or appropriate regimen selected by the investigator).

Treatment Group 3

Participants in Treatment Group 3 who complete the study through Week 52 with HIV-1 RNA < 50 copies/mL at the preceding Week 50 visit and in the absence of confirmed VR (as defined in Section 6.3.9.2.2) throughout the randomized phase of the study will be given the option to participate in the extension phase and receive the study drugs of LEN, GS-5423, and GS-2872 every 26 weeks at the dose specified for Treatment Group 1. Treatment with LEN, GS-5423, and GS-2872 will start at Week 52 and at that time the baseline oral ART will be discontinued.

3.2. Duration of Intervention

Participants who are eligible to participate may receive up to 52 weeks of treatment during the randomized phase. Participants who are eligible to participate in the extension phase have the option to continue to receive study drug until the product becomes accessible to participants through an access program, is commercially available, or Gilead elects to discontinue the study, whichever occurs first.

3.3. Protocol-Specific Discontinuation Criteria

3.3.1. Criteria for Early Discontinuation for the Individual Participants

3.3.1.1. Criteria for Early Discontinuation for the Individual Participant From Study Intervention

Study interventions will be discontinued in the following instances:

- An AE that would, in the judgment of the investigator, affect assessments of clinical status to a significant degree.
 - Following resolution of the AE, the participant may resume study dosing at the discretion of the investigator.
- Unacceptable toxicity, such as a Grade 3 or higher infusion-related reaction to GS-5423 or GS-2872, per Common Terminology Criteria for Adverse Events (CTCAE) grading scale as defined in Section 7.6, or toxicity that, in the judgment of the investigator, compromises the ability to continue study-specific procedures or is considered not to be in the participant's best interest.
- Lack of efficacy: confirmed VF with emergent resistance to study drugs (refer to Section 6.3.9.2).
- Participant request to discontinue for any reason.
- Participant noncompliance.
- Pregnancy during the study; refer to Appendix 11.3.

- Loss to follow-up.
- Discontinuation of the study by sponsor.

3.3.1.2. Criteria for Early Discontinuation for the Individual Participant From the Study

The participant will be discontinued from the study early in the following instances:

- Withdrawal of consent
- Death
- Investigator decision to remove participant from the study
- Loss to follow-up (see Section 3.3.3)
- Discontinuation of study at the request of Gilead

3.3.2. Criteria for Early Discontinuation of the Study

The study will be discontinued in the following instance:

- Discontinuation of the study at the request of Gilead, regulatory agency, or an institutional review board (IRB).

3.3.3. Loss to Follow-up

Should the participant fail to return to the investigational site for a scheduled protocol-specific visit, sites will need to make at least 2 attempts by a combination of phone and certified mail to contact the participant. Sites must document both attempts to contact the participant. If a participant is contacted, the participant should be counseled on the importance of maintaining the protocol-specified visit scheduled. If a participant does not respond within 4 weeks after the second contact, the participant will be considered lost to follow-up and no additional contact will be required.

3.4. Definitions for Time of Primary Endpoint and End of Study

3.4.1. Primary Endpoint

The date for the last participant visit for the primary endpoint is the date of the last visit to perform assessments for the primary analysis.

3.4.2. End of Study

The end of this study will be the last participant's last observation (or visit).

3.5. Poststudy Care

Once a participant has completed their study participation, the long-term care of the participant will return to the responsibility of their primary treating physicians.

3.6. Source Data

The source data for this study will be obtained from participants clinical/hospital records, central laboratory, specialty laboratory (eg, for PK/ADA and/or pharmacodynamic data), eCOA, and interactive response technology (IRT) data.

4. PARTICIPANT POPULATION

4.1. Number of Participants and Participant Selection

Approximately 75 participants who are sensitive to both GS-5423 and GS-2872 by protocol-defined criteria and who meet the eligibility criteria will be randomized without stratification in a 2:1 ratio to Treatment Groups 1 and 3. The collection of race and ethnicity information allows for the analysis and reporting of study data by demographic subgroups as required by certain health authorities.

4.1.1. Participant Replacement

Participants who discontinue before the end of the study will not be replaced.

4.2. Inclusion Criteria

Participants must meet all of the following inclusion criteria to be eligible for participation in this study:

- 1) The ability to understand and sign a written informed consent form (ICF), which must be obtained prior to initiation of study procedures.
- 2) Between 18 and 65 years of age, inclusive, at screening.
- 3) Body weight \geq 40 kg at Screening Visit 2.
- 4) On stable oral ART consisting of no more than 2 drug classes (with the exception of pharmacologic boosters cobicistat or ritonavir) for \geq 1 year prior to Screening Visit 2. A change in ART regimen \geq 28 days prior to Screening Visit 2 for reasons other than VF (eg, tolerability, simplification, drug-drug interaction profile) is allowed.
- 5) No clinically significant documented historical resistance to the current ART regimen with the exception of isolated nucleoside reverse transcriptase inhibitor mutations including M184V or \leq 2 thymidine analog mutations (TAMs: M41L, D67N, K70R, L210W, T215Y, and/or K219Q).
- 6) Plasma HIV-1 RNA $<$ 50 copies/mL at Screening Visit 2.
- 7) Documented plasma HIV-1 RNA $<$ 50 copies/mL for \geq 12 months preceding Screening Visit 2 (or undetectable HIV-1 RNA level according to the local assay being used if the limit of detection is \geq 50 copies/mL). Virologic elevations of \geq 50 copies/mL (transient detectable viremia or “blips”) prior to screening are acceptable.
 - A) If HIV-1 sensitivity testing results are from $>$ 12 months prior to screening (Inclusion Criterion 8), then documented plasma HIV-1 RNA $<$ 50 copies/mL encompassing the time from sensitivity testing will be required.

- 8) HIV-1 sensitivity results from screening or from the Study GS-US-536-5816 within 36 months prior to Screening Visit 2 meeting specific criteria:
 - A) Proviral phenotypic sensitivity to both GS-5423 and GS-2872 by the PhenoSense Assay (Monogram Biosciences). GS-5423 phenotypic sensitivity is defined as 90% inhibitory concentration ($IC_{90} \leq 2 \mu\text{g/mL}$; GS-2872 phenotypic sensitivity is defined as $IC_{90} \leq 2 \mu\text{g/mL}$.
- 9) CD4+ T-cell count ≥ 200 cells/ μL at Screening Visit 2.
- 10) Availability of a fully active alternative ART regimen, in the opinion of the investigator, in the event of discontinuation of the current ART regimen with development of resistance.
- 11) Estimated glomerular filtration rate (eGFR) ≥ 30 mL/min according to the Modification of Diet in Renal Disease formula {[Lacombe 2008](#), [Levey 2006](#)}.
- 12) All of the following laboratory results at Screening Visit 2:
 - A) Alanine aminotransferase (ALT) and aspartate aminotransferase (AST) $\leq 5 \times$ upper limit of normal (ULN).
 - B) Total bilirubin ≤ 1.5 mg/dL, or normal direct bilirubin.
 - C) Absolute neutrophil count $\geq 750/\text{mm}^3$; (chronic neutropenia with no clinical significance can enroll at investigator discretion).
 - D) Platelets $\geq 50,000/\text{mm}^3$; and hemoglobin ≥ 8.5 g/dL.
- 13) Participants assigned female at birth of childbearing potential (as defined in [Appendix 11.3](#)) must have a negative serum pregnancy test at Screening Visit 2 and negative urine pregnancy test at Day 1 prior to study drug administration.
- 14) Participants assigned female at birth of childbearing potential who engage in heterosexual intercourse must agree to utilize protocol-specified method(s) of contraception as described in [Appendix 11.3](#).

4.3. Exclusion Criteria

Participants who meet any of the following exclusion criteria are not eligible to be enrolled in this study:

- 1) Any prior receipt of LEN or a bNAb for HIV-1 treatment.
- 2) Receipt of long-acting injectable ARV within 6 months of Screening Visit 2.

- 3) Have been treated with immunosuppressant therapies or chemotherapeutic agents (eg, corticosteroids, immunoglobulins, and other immune- or cytokine-based therapies) within 4 weeks of Screening Visit 2 (with the exception of a single short course of corticosteroids lasting ≤ 7 days) or have a comorbid condition with an anticipated need ongoing immunosuppressive treatment during the study.
- 4) Pregnant participants assigned female at birth or plans to become pregnant during the course of the study.
- 5) Lactating participants assigned female at birth.
- 6) Participation in any other clinical study, including observational studies, without prior approval from the sponsor.
- 7) Clinically significant abnormal electrocardiogram (ECG) at the Screening Visit 2.
- 8) Hepatitis C virus (HCV) antibody positive and HCV RNA detectable.
- 9) Chronic hepatitis B virus (HBV) infection, as determined by either: positive HBV surface antigen and negative HBV surface antibody, regardless of HBV core antibody status, at the screening visit, or positive HBV core antibody, negative HBV surface antibody regardless of HBV surface antigen status, at Screening Visit 2.
- 10) Active, serious infections (other than HIV-1 infection) requiring systemic antibiotic or antifungal therapy within 30 days prior to Screening Visit 2.
- 11) Have poor venous access that would limit phlebotomy or IV infusion of study drugs.
- 12) Have a history of any of the following:
 - A) Opportunistic infection or illness indicative of Stage 3 HIV disease.
 - B) Known hypersensitivity to the study drug, the metabolites, or formulation excipient.
 - C) Malignancy within the past 5 years (prior to screening) or ongoing malignancy, other than basal cell carcinoma, or resected, noninvasive cutaneous squamous carcinoma.
 - D) Substance abuse or a psychiatric or medical condition that could, in the opinion of the investigator, compromise the participant's ability to participate in the study.

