Eleven participants were enrolled into the pilot cohort and received the complete study drugs (5 in the GS-2872 10 mg/kg group and 6 in the GS-2872 30 mg/kg group). One participant restarted ART on Day 30 due to a protocol violation (chronic hepatitis B infection) and continued on study; they are included in the safety analyses but excluded from the efficacy analyses. The median age of participants was 49 years (range: 28 to 63); 8 participants (73%) were assigned male at birth; and all had HIV-1 RNA < 50 copies/mL; and at baseline, all except 1 participant had CD4 cell count ≥ 500 cells/ μ L.

The primary endpoint was the incidence of TESAEs through Week 26. There was 1 TESAE and no Grade 2 or higher adverse events (AEs) related to study drug. There were no TEAEs leading to discontinuation of study drug or study and no deaths. There was 1 TESAE of soft-tissue infection, which was not related to study drug or procedures. The most common TEAEs were ISRs related to administration of SC LEN injections. There were no infusion-related reactions and no treatment-emergent laboratory abnormalities that were Grade 3 or 4. There was no observed difference in safety events between the 2 treatment groups.

Efficacy was assessed at Week 26 according to the US FDA snapshot algorithm. At Week 26, 2 of 4 participants (50%) in the GS-2872 10 mg/kg treatment group and 0 of 6 participants in the GS-2872 30 mg/kg treatment group had HIV-1 RNA ≥ 50 copies/mL. The 2 participants had VR with HIV-1 RNA of 72 and 55 copies/mL respectively at Week 26; neither met the criteria for confirmed VF (HIV-1 RNA ≥ 200 copies/mL on consecutive tests).

The mean (SD) CD4 cell counts at baseline were as follows: GS-2872 10 mg/kg group 1017 (628.7) cells/ μ L; GS-2872 30 mg/kg group 957 (189.1) cells/ μ L. The CD4+ T-cell count was maintained at Week 26 for both treatment groups.

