5.3. Dosage and Administration

Treatment Group 1

Dose and administration of LEN, GS-5423, and GS-2872 for Treatment Group 1 are described below and in [Table 4](#).

Day 1:

Participants will receive the following study drugs. All study drugs should be administered on the same day (ie, no visit window is permitted for Day 1 study drug administration).

- Oral LEN 600 mg will be administered orally with approximately 240 mL water, without regard to food.
- SC LEN 927 mg will be administered within 30 minutes after oral LEN, as 2 SC injections at separate injection sites in the abdomen, within 15 minutes.
- GS-5423 2550 mg IV infusion will be administered immediately following (up to 1 hour after) the last SC LEN injection. Infusions of GS-5423 will be administered over 30 minutes.
- GS-2872 2550 mg IV infusion will be administered at least 15 minutes following (up to 1 hour after) the completion of GS-5423 IV infusion. Infusions of GS-2872 will be administered over 30 minutes.

Participants will discontinue their baseline oral ART following administration of the complete study drugs on Day 1.

Day 2:

Participants will self-administer oral LEN 600 mg at home with approximately 240 mL water, without regard to food, at approximately the same time as the oral LEN dose for loading on Day 1.

Weeks 26 and 52:

Virologic suppression (HIV-1 RNA < 50 copies/mL) from the preceding visit must be confirmed prior to proceeding with dosing visits.

Infusions of GS-5423 and GS-2872 will be sequentially administered following SC LEN injection:

- LEN 927 mg, as 2 SC injections at separate injection sites in the abdomen, within 15 minutes
- GS-5423 IV infusion of 2550 mg
- GS-2872 IV infusion of 2550 mg

Every 26 Weeks During the Extension Phase:

At each dosing visit during the extension phase, the following study drugs will be administered:

- LEN 927 mg, as 2 SC injections at separate injection sites in the abdomen, within 15 minutes
- Infusions of GS-5423 and GS-2872 can either be coadministered (preferred option) or administered sequentially (investigator discretion) following SC LEN injection:

— Coadministration

- GS-5423 2550 mg CCI
GS-2872 2550 mg CCI
IV infusion CCI

— Sequential administration

- GS-5423 2550 mg CCI [REDACTED]
[REDACTED] Infusions of GS-5423 will be administered over 30 minutes.
- GS-2872 2550 mg CCI [REDACTED]
[REDACTED] Infusions of GS-2872 will be administered over 30 minutes.

Table 4. Treatment Group 1 Treatment Table

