Study Day	Treatment Group 1
Day 1	LEN 600 mg (two 300-mg tablets, PO) LEN 927 mg (two 1.5-mL injections, SC) GS-5423-2550 mg (IV infusion) GS-2872-2550 mg (IV infusion)
Day 2	LEN 600 mg (two 300-mg tablets, PO)
Weeks 26 and 52	LEN 927 mg (two 1.5-mL injections, SC) GS-5423-2550 mg (IV infusion) GS-2872-2550 mg (IV infusion)
Every 26 weeks during the extension phase	LEN 927 mg (two 1.5-mL injections, SC) GS-5423-2550 mg CCI [REDACTED] GS-2872-2550 mg CCI [REDACTED]

IV = intravenous; LEN = lenacapavir; PO = orally; SC = subcutaneous

Treatment Group 3

Day 1 Through Week 52:

Participants in Treatment Group 3 will stay on their baseline oral ART through Week 52.

Week 52:

Participants in Treatment Group 3 who are eligible and elect to participate in the extension phase will receive the study drugs of LEN, GS-5423, and GS-2872 as described below and in [Table 5](#).

Participants will receive the following study drugs. All study drugs should be administered on the same day (ie, no visit window is permitted for Week 52 study drug administration):

- Oral LEN 600 mg will be administered orally with approximately 240 mL water, without regard to food.
- SC LEN 927 mg will be administered within 30 minutes after oral LEN for loading, as 2 SC injections at separate injection sites in the abdomen, within 15 minutes.
- Infusions of GS-5423 and GS-2872 will either be coadministered (preferred option) or administered sequentially (at investigator discretion) following SC LEN injection:

— Coadministration

- GS-5423 2550 mg and GS-2872 2550 mg CCI

Infusions of GS-5423 and GS-2872 will be administered over 60 minutes.

— Sequential administration

- GS-5423 2550 mg CCI

Infusions of GS-5423 will be administered over 30 minutes.

- GS-2872 2550 mg CCI

Infusions of GS-2872 will be administered over 30 minutes.

Participants will discontinue their baseline oral ART following administration of the complete study drugs on Week 52.

Week 52 + 1 Day:

Participants will self-administer oral LEN 600 mg at home with approximately 240 mL water, without regard to food, at approximately the same time as the oral LEN dose on Week 52.

Every 26 Weeks During the Extension Phase:

At each dosing visit during the extension phase, the following study drugs will be administered:

- LEN 927 mg, as 2 SC injections at separate injection sites in the abdomen, within 15 minutes

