5.4. Prior and Concomitant Medications

Clinical data indicate LEN is a substrate of cytochrome P450 enzyme (CYP) 3A enzymes, P-glycoprotein (P-gp) transporters, and uridine diphosphate glucuronosyltransferase 1A1 (UGT1A1) enzymes. Lenacapavir is a moderate inhibitor of CYP3A. Lenacapavir is an inhibitor of P-gp and breast cancer resistance protein (BCRP). Concomitant use of LEN with some medications or herbal/natural supplements that are inhibitors or inducers of CYP3A, UGT1A1, or P-gp may result in increased or decreased LEN exposure, respectively. Concomitant use of LEN with some medications or herbal/natural supplements that are substrates of CYP3A, P-gp, or BCRP may result in increased exposure of these medications.

Representative medications listed in Table 6 and herbal/natural supplements are currently excluded or should be used with caution while participating in this study; this table is not exhaustive. Please consult LEN labeling for complete and up-to-date information. Any medication that is not on the list should be reviewed by the medical monitor prior to screening and throughout the study. Vitamins, acetaminophen, ibuprofen, and hormonal medications are allowed during the study period. Participants should discontinue disallowed concomitant medications 30 days prior to initiation of study drug, unless otherwise specified.

Vaccinations should not be administered within 14 days prior to infusion of GS-5423 and GS-2872.

Table 6. List of Representative Medications That are Prohibited or To Be Used With Caution Due to the Potential for Drug-Drug Interaction With LEN

Medication Class	Prohibited Medications	Use Discouraged and To Be Used With Caution
Anticoagulants	—	Dabigatran etexilate: monitoring and/or dose reduction may be needed for certain populations per prescribing information.
Anticonvulsants	Carbamazepine, oxcarbazepine, phenobarbital, phenytoin	—
Antimycobacterials	Rifampin, rifabutin, rifapentine	—
Antiretroviral agents	Any ARV not part of the study treatment regimen	—
Digoxin	—	Digoxin: concomitant use may result in increased levels of digoxin; use with caution and with appropriate monitoring of serum digoxin levels.
Ergot derivatives	Ergotamine, ergonovine, dihydroergotamine, methylergonovine, ergometrine	—
Herbal/natural supplements	St John's wort, echinacea, milk thistle (ie, silymarin), Chinese herb sho-saiko-to (or Xiao-Shai-Hu-Tang)	—

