6.3.5. Clinical Laboratory Assessments

Blood and urine samples will be collected throughout the study as outlined in [Table 1](#), [Table 2](#), and [Table 3](#). Laboratory assessments are listed in [Table 7](#).

Table 7. Laboratory Analytes

Safety Laboratory Measurements			Other Laboratory Measurements
Chemistry (Serum or Plasma)	Hematology	Urinalysis	
ALT AST Alkaline phosphatase Gamma-glutamyltransferase Total bilirubin Direct bilirubin Indirect bilirubin Total protein Albumin Lactate dehydrogenase Creatinine phosphokinase Bicarbonate Blood urea nitrogen Calcium Chloride Creatinine Glucose Phosphorus Magnesium Potassium Sodium Uric acid Amylase Lipase Thyroid-stimulating hormone	CBC	Color & clarity Specific gravity pH Glucose Ketones Urobilinogen Blood Nitrate Leukocyte esterase Protein Uric acid Pregnancy test	Serum pregnancy test Serum FSH CD4+ and CD8+ T-cell count, and CD4/CD8 ratio Proviral DNA phenotype and genotype Plasma HIV-1 RNA HIV-1 Genotype/Phenotype HBcAb, HBsAg, HBsAb, HCVAb, HCV RNA HIV reservoir assay Immunogenicity (ADA) serum sample Plasma storage samples Pharmacokinetics

ADA = antidrug antibody; ALT = alanine aminotransferase; AST = aspartate aminotransferase; CBC = complete blood count; CD4 = clusters of differentiation 4; CD8 = clusters of differentiation 8; FSH = follicle-stimulating hormone; HIV = human immunodeficiency virus; HIV-1 = human immunodeficiency virus type 1; HBcAb = hepatitis B core antibody; HBsAb = hepatitis B surface antibody; HBsAg = hepatitis B surface antigen; HCV = hepatitis C virus; HCVAb = hepatitis C virus antibody; RNA = ribonucleic acid

Refer to [Table 1](#), [Table 2](#), and [Table 3](#) for collection time points.

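### Both limbs of the hepatitis B exclusion need a negative surface antibody, so a person positive for both surface antigen and surface antibody is not excluded

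*Protocol*

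**What the plan says.** Criterion 9 in Protocol Section 4.3, repeated in the synopsis, opens with "Chronic hepatitis B virus (HBV) infection, as determined by either" and then gives two limbs:

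- Limb 1: "positive HBV surface antigen and negative HBV surface antibody, regardless of HBV core antibody status, at the screening visit".
- Limb 2: "positive HBV core antibody, negative HBV surface antibody regardless of HBV surface antigen status, at Screening Visit 2".

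Table 7 (Section 6.3.5) lists the hepatitis tests as "HBcAb, HBsAg, HBsAb, HCVAb, HCV RNA". HBV DNA is not among them. The procedures tables schedule HBV serology once, at Screening Visit 2.

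Section 5.3 takes participants off their own regimen. For Group 1: "Participants will discontinue their baseline oral ART following administration of the complete study drugs on Day 1". For Group 3 participants who enter the extension: "Participants will discontinue their baseline oral ART following administration of the complete study drugs on Week 52". Table 6 (Section 5.4) prohibits "Any ARV not part of the study treatment regimen".

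Section 1.2.4 describes a case in the Phase 1b pilot cohort: "One participant restarted ART on Day 30 due to a protocol violation (chronic hepatitis B infection) and continued on study". That participant was left out of the efficacy analyses.

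**The concern.** The criterion is headed as an exclusion of chronic HBV, and limb 1 treats a positive surface antigen as enough to establish it even when core antibody is negative. Yet a positive surface antibody cancels that result, even when core antibody is also positive. The phrases that release a marker cover core antibody in limb 1 and surface antigen in limb 2. Neither limb releases surface antibody.

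A person with this serology who is otherwise eligible can be randomized, lose the baseline regimen and be barred from other antiretrovirals. The first stake is that individual's safety. The protocol does not describe the clinical course after withdrawal, but the sponsor's handling of the Phase 1b case shows that it regards chronic HBV as incompatible with being off ART. The second, smaller stake is data: SAP Section 6 ends on-treatment data for Group 1 at the ART restart date, so a restart forced by HBV affects the snapshot outcome.

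**Working it through.** **Step 1. Apply criterion 9 to every serology pattern.** A person is excluded if (antigen positive and surface antibody negative) or (core antibody positive and surface antibody negative).

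| Surface antigen | Surface antibody | Core antibody | Limb 1 | Limb 2 | Result |
|---|---|---|---|---|---|
| + | + | + | no | no | not excluded |
| + | + | - | no | no | not excluded |
| + | - | + | yes | yes | excluded |
| + | - | - | yes | no | excluded |
| - | + | + | no | no | not excluded |
| - | + | - | no | no | not excluded |
| - | - | + | no | yes | excluded |
| - | - | - | no | no | not excluded |

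Three of 8 patterns are excluded. Of the 4 antigen-positive patterns, 2 pass. Every pattern with a positive surface antibody passes.

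**Step 2. Look for another criterion that closes the gap.** Exclusion 10 concerns infections needing systemic antibiotic or antifungal therapy. Inclusion 12A permits ALT and AST up to 5 x ULN. No criterion uses HBV DNA, whereas the HCV exclusion (criterion 8) does use HCV RNA. Exclusion 12D allows exclusion for a medical condition in the investigator's opinion; it is discretionary and does not name HBV.

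**Step 3. Trace the effect on the Week 26 snapshot (SAP 6.1.2).** The Group 1 window is Study Day 176 to 224. Suppose a participant restarts ART before Day 176 for a reason other than lack of efficacy, with the last on-treatment HIV-1 RNA below 50 copies/mL and no on-treatment value in the window. The outcome is No Virologic Data. The participant stays in the Full Analysis Set denominator, taken as the planned 50:

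- primary proportion, at or above 50 copies/mL: 0/50 = 0 points added;
- secondary proportion, below 50 copies/mL: 1/50 = 2 points lost.

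Group 3 stays on baseline ART through Week 52, so the gap does not withdraw ART from this group in the randomized comparison.

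**Step 4. Illustrate the frequency.** The documents give none. Purely as an assumption, let 1% to 5% of people screened be antigen positive and 2% to 10% of those also be surface-antibody positive.

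- Low end: 0.01 x 0.02 = 0.0002; x 75 = 0.015 expected cases; chance of none = 0.9998^75 = 0.985.
- High end: 0.05 x 0.10 = 0.005; x 75 = 0.375 expected cases; chance of none = 0.995^75 = 0.687.

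**Step 5. Ask whether planned outputs would reveal a case.** SAP 4.5 lists participants who failed an eligibility criterion; this person failed none. SAP 5.2 does not include HBV serology among baseline characteristics. SAP 7.2 specifies laboratory listings for hematology, serum chemistry and urinalysis. None of these is designed to show the pattern.

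**The case against.** The strongest objection is timing. Protocol Section 1.4.1.2 already reports Week 26 and Week 52 results, and Section 4.1.1 rules out replacement, so enrolment appears complete and rewording cannot change who was randomized. That stands. It shifts the weight to the data query. It does not remove the point, because extension participants remain off baseline ART and Section 6.2 makes investigators responsible for continued eligibility.

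The second objection is that safeguards exist: all three markers are known before randomization, 12D is available, and eligibility questions can go to the medical monitor. This is fair, but all of it is discretionary, and the written rule returns a pass.

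Several stronger readings are tempting and are not supported:

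- *That 1 of 11 in the Phase 1b pilot cohort shows how often this gap operates.* That participant was a protocol violation under another study's criteria, with serology not given. The case shows only that chronic HBV led to an ART restart and exclusion from efficacy.
- *That each case moves the primary endpoint by 2 points.* Step 3 shows 0 points on the primary in the scenario described; the 2 points fall on the secondary proportion.
- *That a restart removes all later HIV-1 RNA results.* It removes them from on-treatment analyses. The by-visit missing-equals-failure and missing-equals-excluded analyses (SAP 6.3.2.1) use all data collected in the randomized phase.
- *That the two visit terms create a real operational ambiguity.* Serology is scheduled only at Screening Visit 2, so the mismatch is editorial.

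**Conclusion.** The gap is real on the literal text, in both Section 4.3 and the synopsis: a person positive for surface antigen and surface antibody is not excluded, and only investigator discretion could exclude them. It is a wording defect with a potentially serious consequence for an individual and little expected effect on the trial's estimates.

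Zero cases among 75 is the most likely number; this rests on the assumed rates in Step 4, not on the documents. The 0-point and 2-point figures assume 50 in the Group 1 Full Analysis Set, a restart before the Week 26 window while suppressed, a reason other than lack of efficacy, and no on-treatment value in the window. That a particular participant's baseline regimen was also controlling HBV is not stated anywhere and would have to be established case by case.

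**What to change.** 1. Reconcile the two limbs of criterion 9, in Section 4.3 and the synopsis, with the stated purpose of excluding chronic HBV. The handling of a positive surface antigen with a positive surface antibody should be explicit and should not default to eligible. The clinical rule itself is for the sponsor to settle.
2. Replace limb 1's reference to the screening visit with Screening Visit 2.
3. Query the Screening Visit 2 serology already held for any antigen-positive randomized participant. Show any case that is also surface-antibody positive in a separate listing and bring it to the medical monitor. It should not be reported as an SAP 4.5 eligibility deviation, because that person meets the criteria as written. An antigen-positive, antibody-negative participant already fails criterion 9 and belongs under SAP 4.5.

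The cost is one clause and one listing, with no new test. If the criterion is tightened, a rare person with a transient antigen result may be excluded or need retesting.
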